3 OBJECTIVES AND ENDPOINTS

OBJECTIVES	ENDPOINTS	JUSTIFICATION FOR ENDPOINTS
Primary		
To determine the relationship between endemic infections, immune activation (IA), T cell zone (TZ) fibrosis with loss of the fibroblastic reticular cell network (FRCn), CD4 and CD8 T cell subsets and the magnitude and durability of neutralizing antibody response to YFV in a cohort shown to have elevated IA,	Peak titer of neutralizing antibody to yellow fever vaccination	The primary analysis endpoint is the peak titer of neutralizing antibody. We believe that there will be significant differences in the peak titer and durability of titers between the two groups.

OBJECTIVES	ENDPOINTS	JUSTIFICATION FOR ENDPOINTS
a damaged FRCn, and pan T cell depletion and a cohort that does not.		
Secondary		
To determine predictors of levels of neutralizing antibodies	
 1. Measures of T cell zone fibrosis (collagen and desmin) 2. Measures of past and present infection (pathseq, molecular analyses of helminth infection and serum antibody studies) 3. Measures of immune activation (Ki67+ and CD69 + cells) 4. Measures of systemic and lymphatic inflammation (plasma cytokines, frequency of TGFβ+ and TNF+ cells in lymphoid tissues). 5. Changes in T cell number and function 	We believe the reason that titers will be different is that inflammation from endemic infections alters the architecture and therefore the function of the lymphatic tissues which results in less antibody being made. With these secondary endpoints we will measure these potential predictors.
Tertiary/Exploratory		
To determine the impact of LN fibrosis on specific T cell populations including T follicular helper cells and antigen specific T cells.	
 1. Histologic analyses of lymphoid tissues for T follicular helper cells and B cells. 2. Size and change to the frequency of yellow fever antigen specific CD4+ T cell population. 	We have shown that lymphatic tissue fibrosis causes depletion of CD4 and CD8 + T cells however we have never examined the impact on highly specific subsets.

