9 STATISTICAL CONSIDERATIONS

9.1 STATISTICAL HYPOTHESES

- Primary Efficacy Endpoint(s):

Null hypothesis: There is no difference in peak yellow fever antibody titer between individuals from the US and Uganda.

Alternative hypothesis: There is a difference in peak yellow antibody titer.

- Secondary Efficacy Endpoint(s):

Null hypothesis: There is no difference in baseline LN architecture measures (TZ collagen, FRCn, B cell follicles and populations, Tfh cells, and B Cell activating factor) between individuals from the US and Uganda. Alternative hypothesis: There are differences in these measures between the two countries.

Null hypothesis: There is no association between baseline measures of LN architecture and rate of YFV antibody decay. Alternative hypothesis: There are associations between these measures and rate of antibody decay.

Null hypothesis: Principal components of pathseq data are not associated with country of origin.

Alternative hypothesis: Some principal components of pathseq data are be associated with country.

Null hypothesis: There are no difference in helminth infection patterns between the US and Uganda.

Alternative hypothesis: Differences in helminth infections exist between the two countries.

Null hypothesis: Pathseq principal components with strong loadings for infection organisms are not associated with baseline measures of LN architecture. Alternative hypothesis: PC components with strong loadings for infectious organisms are associated with baseline LN architecture measures.

Null hypothesis: Presence of helminth infection is not associated with baseline LN architecture measures. Alternative hypothesis: Presence of helminth infection is associated with baseline LN architecture measures.

Null hypothesis: There is no association between changes in immune function after vaccination and measures of LN architecture. Alternative hypothesis: There is an association between change in immune function and measures of LN architecture.

Null hypothesis: There is no association between CD4, CD8 functional variables and CD4 subsets and peak YFV antibody titers or rate of antibody decay. Alternative hypothesis: There is an

association between CD4, CD8 functional variables and CD4 subsets and peak YFV antibody titers and rate of antibody decay.

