Null hypothesis: There is no association between CD4, CD8 functional variables and CD4 subsets and peak specific IgM, IgG1, IgG2, IgG3 and IgG4 responses or rate of change. Alternative hypothesis: There is an association between CD4, CD8 functional variables and CD4 subsets and peak specific IgM, IgG1, IgG2, IgG3 and IgG4 responses or rate of change.

Null hypothesis: There is no change in immune activation or inflammation measures or CD4 and CD8 cells after immunization. Alternative hypothesis: There is a change in immune activation or inflammation measures or CD4 and CD8 cells after immunization.

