9.4.3 ANALYSIS OF THE SECONDARY ENDPOINT(S)

Differences in rate of YFV antibody titer decay will be compared between vaccinated Ugandans and Minnesotans using linear mixed effects regression model with measurement time, country, and the interaction between measurement time and country as predictors. Baseline LN measures (area with collagen, area with desmin staining, frequency and size of B cell follicles, and frequency of Tfh cells) will be compared between the two countries using Mann-Whitney U tests.

We will examine the association between vaccine response over time and baseline LN measures using linear mixed effects models adjusting for measurement time and gender.

To examine differences in infection patterns between the two countries, we will perform principal component analyses on the baseline pathseq data. We will test for differences in infection patterns between Uganda and the US populations using logistic regression with country as the outcome and the scores for each of the first five principal components as predictors. Differences in helminth infections between Ugandans and Minnesotans will be compared using Fisher's exact test.

We will examine the association between infection history and baseline LN architecture by fitting separate linear regression models for each measure of baseline LN architecture with gender and the 5 pathseq principal component scores as predictors. The association between helminth infections and baseline LN architecture measures will be assessed using Mann-Whitney U tests.

To elucidate the role of previous infections on inflammation and activation we will use sparse canonical correlation analysis (Reference: Witten, D., Tibshirani, R., & Hastie, T. (2009). A penalized matrix decomposition, with applications to sparse principal components and canonical correlation analysis. *Biostatistics*, 10(3), 515-534.) to identify sets of organismal sequences correlated with baseline measures of systemic and lymphatic inflammation (plasma cytokines, frequency of TGF β + and TNF+ cells in lymphoid tissues) and immune activation (Ki67+ and CD69 + cells). The association between helminth infection and measures of inflammation and activation be assessed using a logistic lasso regression model. Measures which have non-zero coefficients in the model will be considered associated with helminth infection.

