The association between change in measures of CD8 function (IFN γ , TNF α , and IL-2) after vaccination and measures of LN architecture will be examined by fitting mixed effects linear models using area with collagen staining, area with desmin staining, and measurement time and gender as predictors.

The association between immune function after vaccination and measures of inflammation and activation will be assessed using separate lasso regression for each measure of immune function (antigen specific CD4, CD8 function measures, and CD4 and CD8 subpopulations). Inflammation and activation measures which have non-zero coefficients in the model will be considered predictive of immune function.

We will examine the impact of measures of immune function on YFV response using separate mixed effects linear models with gender, measurement time and measures of immune function (antigen specific CD4, CD8 functional variables, or CD4 and CD8 subpopulations) as predictors. Similar models will be fit for YF specific IgM, IgG1, IgG2, IgG3 and IgG4 responses.

The impact of vaccination on measures of inflammation and activation be assessed using mixed effects repeated measures model with gender, measurement time, and vaccination status as predictors. To assess the impact of vaccination on CD4 and CD8 cells in LT similar models will be fit, but only gender and vaccination status (measurement taken before or after vaccination) will be used as predictors.

Missing data will not be imputed and a significance level of 0.01 will be used for secondary analyses due to the large number of hypotheses to be tested. The results from all of these investigations will be reported so that the reader can assess the effect of multiple hypothesis testing.

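### The lymph node model for titer over time has no LN-by-time term, so it does not test the stated hypothesis on rate of antibody decay; the decay analyses also lack a stated post-peak start visit

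*Combined protocol and SAP*

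**What the plan says.** One of the secondary null hypotheses in Section 9.1 reads: "There is no association between baseline measures of LN architecture and rate of YFV antibody decay". In Section 9.4.3 the only analysis that links LN measures to titer examines vaccine response over time and "baseline LN measures using linear mixed effects models adjusting for measurement time and gender". No product of LN measure and time is named.

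The paragraph before it, on decay by country, specifies a "linear mixed effects regression model with measurement time, country, and the interaction between measurement time and country as predictors". So the plan writes out a time interaction where it intends one.

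Section 9.4.1 adds subject-specific random effects and permutation p-values to all mixed models. Section 9.3 limits the titer analyses to vaccinated participants; it does not limit sampling times. No section gives a start visit for the decay models.

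Section 8.2 lists titers through Days 3 to 14, on Day 17, at Week 8 and at Month 18. The Schedule of Activities, as it reads in the extracted text, marks Days 1, 3, 5, 7, 10, Week 3, Week 8 and Month 18 after screening. Section 2.2 reports the preliminary Ugandan peak at Week 3. Section 3 states: "We believe that there will be significant differences in the peak titer and durability of titers between the two groups".

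**The concern.** The hypothesis is about a slope and the model estimates a level. Section 2.2 reports that participants with more of the fibroblastic reticular cell network had higher peak titers. An LN measure of that kind, related to peak and not to decay, would tend to be significant in the only model matched to the decay hypothesis and could be reported as evidence on durability. A measure related only to decay would usually be missed. Durability is part of the primary objective, so this distinction matters to the trial's conclusions.

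The second part concerns the time window. A model of decay needs samples from after the peak, and many of the scheduled titers are taken before or during the rise. If they were included with linear time, part of any difference in peak height would be counted as a difference in slope. The plan expects the countries to differ in peak.

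**Working it through.** **The plan's own figure.** The only power statement is for the primary peak comparison (Section 9.2: 30 vs 16, SD 1, difference 1, two-sided 0.05, over 85%). The noncentrality is 1/√(1/30 + 1/16) = 3.23; with 43 degrees of freedom the power is 88.4%, which agrees. No figure is given for the LN or decay models.

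**What the LN coefficient measures.** As written, for participant i at time t:

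E(titer) = b0 + b1·LN_i + b2·t + b3·gender_i

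The rate of change is b2 for every value of LN. A random slope would add variance around b2 but no dependence on LN. With b4·LN_i·t added, the rate is b2 + b4·LN_i, and b4 is the test of the decay hypothesis. With balanced visits, b1 in the planned model equals the regression of participants' mean titers on LN, and b4 equals the regression of their slopes on LN. A fitted mixed model confirmed both (0.2087 and 0.2087; 0.0137 and 0.0137).

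**Inputs for the illustration.**
- From the plan: n = 46; alpha 0.01 for secondary analyses; person SD 1 ln = 0.434 log10. Natural log is inferred from Section 9.2, where a mean of 7.89 is a titer of about 2,670.
- Inferred: r = 0.516 between LN measure and outcome, from p = 0.02 in Section 2.2 if n = 20: t(18) = 2.55, r = 2.55/√(2.55² + 18).
- Assumed, not in the documents: residual SD 0.2 log10; slope SD 0.3 log10/yr.

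**Week 8 and Month 18 only (35 and 526 days after Week 3).**
- Mean time since peak: 280.5 days = 0.768 yr. Gap between visits: 491 days = 1.344 yr.
- SD of participant mean: √(0.434² + (0.3 × 0.768)² + 0.2²/2) = 0.511.
- SD of participant slope: √(0.3² + 2 × 0.2²/1.344²) = 0.366.
- Peak-only: correlation with the mean 0.516 × 0.434/0.511 = 0.438; with the slope 0.
- Decay-only: correlation with the mean 0.516 × 0.230/0.511 = 0.232; with the slope 0.516 × 0.3/0.366 = 0.423.
- Approximate power by Fisher z, Φ(√42 × atanh(r) − 2.576), where 42 = 46 − 1 − 3 allows for gender: 68%, 15% and 64% for correlations 0.438, 0.232 and 0.423. A zero correlation gives the nominal 1%.

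Simulation agrees:

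| Visits | LN related to | Planned LN term | LN-by-time |
|---|---|---|---|
| Week 8, Month 18 | peak only | about 70% | 1% |
| Week 8, Month 18 | decay only | about 15% | 65% |
| with Week 3 | peak only | about 78% | 1% |
| with Week 3 | decay only | about 7% | 72% |

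Across residual SD 0.1 to 0.3 and slope SD 0 to 0.3 (0.15 to 0.3 for decay-only), peak-only gives 61% to 91% against about 1%, and decay-only 2% to 17% against 13% to 88%. At the low end neither term finds a decay effect. At r = 0.3 the figures are 16% to 30% against about 1%, and 1% to 5% against 4% to 28%.

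**Pre-peak titers.** In Section 8.2 the post-vaccination titers are Days 3, 5, 7, 10, 12, 14, 17, Week 8 and Month 18: 7 of 9 precede Week 3. In the extracted Schedule they are Days 3, 5, 7, 10, Week 3, Week 8 and Month 18: 4 of 7.

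**What including them would do to the country model.** Let f be the fraction of the rise reached at each visit. With equal decay and equal pre-rise level, the false slope difference is the peak difference times the slope of f on time, so the decay rate cancels. Take a rise from Day 7 to Day 21 (assumed), Week 8 as Day 56 and Month 18 as Day 547.
- Section 8.2 visits: f = 0, 0, 0, 0.214, 0.357, 0.5, 0.714, 1, 1. Slope = 0.948/1.897 = 0.500 per yr; × 0.434 = 0.217 log10/yr.
- Schedule visits, with Day 1: f = 0, 0, 0, 0, 0.214, 1, 1, 1. Slope = 0.999/1.875 = 0.533 per yr; × 0.434 = 0.231 log10/yr.
- Rise starting Day 3 to 10 and peak at Day 14 to 28: 0.13 to 0.26 log10/yr.

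From a post-peak visit onward f = 1 throughout and the false difference is 0. The same algebra applies to an LN-by-time term fitted to all visits: a peak-only LN effect would give a false slope of 0.50 to 0.53 times that effect per year.

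**The case against.** **Wording.** The analysis is of response over time, which may hint at a trajectory. But the stated terms are time and gender as adjustments, and random effects do not supply the missing fixed effect. This objection does not stand.

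**Decay already means after the peak.** This is a fair reading, and it limits the second part. The 0.22 arises only if an analyst includes titers from before the peak. A reader might infer that the country comparison will be biased; the documents do not support that. They leave the start visit open, which is a detail to settle before the data are seen.

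**Sign of the slope.** A reader might infer that the fitted decay slope would come out as a rise. That depends on the log unit in Section 2.2, which is not stated. A fall of 0.9 over 57 weeks (1.092 yr) is 0.36 log10/yr if natural log and 0.82 if log10. At 0.36 all 64 shapes tried gave a positive slope; at 0.82, 22 of 64 (Section 8.2 visits) and 15 of 64 (Schedule visits) were negative. The reported range of 1.3 log also fits poorly with SD 1 in the same unit: none of 100,000 normal samples of 20 had so small a range, though censoring at the detection limit could shrink it. No claim about the sign is made.

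**Stored plasma.** Plasma is stored at nearly every visit, so more titers could be assayed. No section commits to this. If all were assayed, the false slope in the base case would fall to 0.19.

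**Scope.** These are secondary analyses, and Section 9.4.3 promises to report all results. This limits the consequence; it does not make the model test its hypothesis.

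**Other models.** A reader might extend the point to all the mixed models in Section 9.4.3. The hypotheses there concern "peak YFV antibody titers or rate of antibody decay" and "peak specific IgM, IgG1, IgG2, IgG3 and IgG4 responses or rate of change", so a level association already bears on part of them. The analyses are "separate mixed effects linear models with gender, measurement time and measures of immune function", and "Similar models will be fit for YF specific IgM, IgG1, IgG2, IgG3 and IgG4 responses". The plan does not say whether those predictors are baseline values. If they vary over time, the question is a different one.

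**Conclusion.** The LN model as written does not test the decay-rate hypothesis of Section 9.1. This follows from its terms and needs no assumption. The size of the mismatch, about 70% against 1% for a peak-only measure and about 15% against 65% for a decay-only measure, rests on r of about 0.52, natural-log units in Section 9.2, and assumed residual and slope SDs.

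The missing start visit is a real but conditional gap. It would matter only if pre-peak titers were included, and then a 1 ln peak difference would appear as about 0.22 log10/yr (0.13 to 0.26 over the rise shapes tried), whatever the true decay rate. The primary peak-titer comparison is not affected by either part.

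**What to change.** 1. Add LN measure × time to the LN titer model and name it as the test of the decay-rate hypothesis.
2. Fit the country and LN decay models only from one pre-stated post-peak visit onward, the same in both cohorts, and state the form of time. First confirm whether a Week 3 titer is drawn: the extracted Schedule of Activities marks one and Section 8.2 does not list it. The Schedule's columns look shifted in extraction (its LN biopsy marks also disagree with Section 8.2), so check the source table.
3. Report association with peak separately, by regression of log peak titer on the LN measure.
4. As an aside, where predictors in the immune-function and immunoglobulin models are baseline values, add predictor × time for the rate half of those hypotheses.

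Items 1 and 2 belong together, since an LN-by-time term fitted to all visits would absorb peak effects.

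**Cost.** SAP wording and one term per model; no new visits or samples. The peak regressions enlarge the family tested at 0.01. Rate terms are less precise with the titers listed: at residual SD 0.2 and slope SD 0.15 to 0.3, the standard error of the country difference in slope is 0.080 to 0.113 log10/yr from Week 8 and Month 18, or 0.071 to 0.108 with Week 3.

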9.3 POPULATIONS FOR ANALYSES

For comparisons involving the primary endpoint, YFV titers, we will only include study participants who received the YF vaccine. For analysis of secondary endpoints, we will use data from all available study participants.

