9.4 STATISTICAL ANALYSES

9.4.1 GENERAL APPROACH

Medians and interquartile ranges will be presented for descriptions of continuous data. Percentages will be presented for categorical data.

Counts of cell frequency and QIA endpoints involving the percent area will be log-transformed and linear regression analyses will be conducted where appropriate. If there are no detectable cells or there is no staining detected for a large portion of study participants logistic regression modeling will be conducted, instead, with presence or absence of the measure being the outcome.

Two-sided tests will be conducted for all comparisons. Subjects specific random effects will be included in all mixed effects models and permutation p-values will be presented. To control for multiple comparisons, a cut-off of alpha=0.01 will be used for determining statistical significance of all secondary endpoints.

Measures which have non-zero coefficients in lasso models will be considered to be associated with the outcome. Measures which have non-zero correlation coefficients after applying sparse canonical correlation analysis will be considered to be correlated with the outcome measure.

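### Three secondary analyses combine Uganda and Minnesota with no country term or stratum, so a positive result cannot be attributed to infection or lymph node damage

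*Combined protocol and SAP*

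**What the plan says.** Section 9.4.3 plans three analyses linking infection to LN architecture and LN architecture to antibody:

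- Helminths and LN: "The association between helminth infections and baseline LN architecture measures will be assessed using Mann-Whitney U tests".
- PathSeq and LN: "fitting separate linear regression models for each measure of baseline LN architecture with gender and the 5 pathseq principal component scores as predictors".
- LN and antibody: the "association between vaccine response over time and baseline LN measures using linear mixed effects models adjusting for measurement time and gender".

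Country appears in none of them. The same section does use it when comparing titer decay between countries, by a "linear mixed effects regression model with measurement time, country, and the interaction between measurement time and country as predictors".

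On populations, Section 9.3 says of titer comparisons that "we will only include study participants who received the YF vaccine", and otherwise: "For analysis of secondary endpoints, we will use data from all available study participants". That the three analyses combine both cohorts is inferred from this and from the absence of any by-country wording. The only stratification planned is by gender, for the primary test (Section 9.4.2). Section 9.4.1 adds: "Subjects specific random effects will be included in all mixed effects models and permutation p-values will be presented". It does not say how the permutation is done.

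For LN and antibody, the null hypothesis in Section 9.1 is that "There is no association between baseline measures of LN architecture and rate of YFV antibody decay". The model in Section 9.4.3 concerns response over time and names no LN-by-time term.

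**The concern.** The plan expects the cohorts to differ at every step of the proposed chain. Section 2.2 reports T cell zone collagen of 12.4% (SD 3.4%) in Ugandans and 4.3% (SD 2.9%) in Minnesotans. Section 9.2 plans on a 1-log difference in peak titer, and Section 9.1 sets up tests of country differences in infection patterns and LN architecture. When predictor and outcome both differ by country, pooling produces an association even if the two are unrelated within each country.

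This matters because the primary objective (Section 3) concerns how infection, LN damage and antibody response are related, and Section 4.2 attributes the cohort differences to endemic infection. A pooled association shows that the quantities vary together across two contrasting cohorts. It cannot separate infection or LN damage from anything else that differs between Uganda and Minnesota. For these three links no planned analysis does so.

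**Working it through.** **The plan's own figure.** The documents give no power or error rate for these analyses. The one related figure is primary power: 30 vs 16, gap 1 log, SD 1, two-sided alpha 0.05. A noncentral t calculation gives 0.884, in line with the stated figure of over 85%. Simulated Mann-Whitney power is 0.861 (normal), 0.864 (gamma, unrounded scales) and 0.838 (shifted t), against the stated 0.871, 0.874 and 0.841. The planning inputs are therefore understood correctly.

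**Inputs.** From the documents: n = 30 and 16, gender balanced; two-sided alpha 0.01 for secondary analyses (Section 9.4.1); collagen means and SDs (Section 2.2); titer SD 1 log and gap 1 log (Section 9.2, a power assumption and not an estimate). Assumed: intraclass correlation (ICC), which visits carry the gap, slope gaps, helminth prevalence and component shifts. Every rate below is the chance of p<0.01 with no within-country association.

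**1. Collagen against a single titer, by hand.** With no within-country link, the pooled correlation is the product of each variable's correlation with country.

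- Country variance: 30×16/46² = 0.2268.
- Collagen: between-country variance 0.2268×(12.4−4.3)² = 14.88; within-country variance (30×3.4²+16×2.9²)/46 = 10.46; correlation √(14.88/25.35) = 0.766.
- Titer: √(0.2268/1.2268) = 0.430.
- Pooled correlation: 0.766×0.430 = 0.33 in size, negative in sign. The simulated mean was −0.33.
- Rejection rate by Fisher's z, allowing for gender: Φ(0.342×√42 − 2.576) = Φ(−0.36) = 36%.

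Simulation (20,000 trials) gives 39% for normal raw collagen, 39% for lognormal raw, 44% for the log of lognormal and 35% for the log of truncated normal. Adding country gives about 1%. At a 0.5-log gap the pooled rate is 8–9%; at 1.5 logs it is 72–83%.

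**2. Repeated titers, level model.** With m visits, of which k carry the 1-log gap, a subject mean has variance ICC+(1−ICC)/m and country gap k/m. For m=7, k=3, ICC 0.5, that is variance 0.5+0.5/7 = 0.571 and a gap of 0.429/√0.571 = 0.57 SD. The schedule of activities as extracted shows 7 post-vaccination antibody visits, 3 of them after Day 10. Section 8.2 describes 9, with 5 after Day 10. ICC is taken as 0.5–0.8.

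| Visits | Visits with gap | Pooled rate |
|---|---|---|
| 7 | 3 | 6–12% |
| 7 | 7 | 43–72% |
| 9 | 5 | 12–23% |
| 9 | 9 | 44–73% |

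With country in the model the rate is about 1% throughout. Permutation p-values help only if permuted within country: with all 7 of 7 visits carrying the gap, unrestricted permutation gives 48–66%; within-country permutation gave 0–1.8% across the scenarios run.

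**3. If the target is decay (LN-by-time).** A level gap constant over the modelled visits gives no excess (0.9–1.1%). An assumed country gap of 0.25, 0.5 or 1 SD of subject slopes gives 2–3%, 7–9% or 35–44%.

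**4. Helminths and PathSeq components (direction only).** Pooled Mann-Whitney of collagen by helminth status:

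| Assumed Uganda prevalence | 10% | 30% | 50% | 70% | 90% |
|---|---|---|---|---|---|
| Minnesota 0% | 1% | 15% | 52% | 89% | 99.8% |
| Minnesota 10% | 0.6% | 4% | 27% | 69% | 98% |

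The country-stratified test stays at or below about 1%. An assumed country shift in the first component of 0.5, 1 or 2 SD gives 7–9%, 35–41% or 92–95%, against about 1% with country.

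**The case against.** The strongest reply is that no planned test fails its stated hypothesis. The nulls in Section 9.1 are marginal, the pooled tests are valid for them, and Section 9.4.3 speaks only of association. The rates above are therefore not type I error rates for any hypothesis in the plan. That stands, and the point here is confined to attribution.

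Second, the cohort contrast is the design. In the proposed chain country lies upstream of infection, so adjusting for it removes variation the study set out to create. If collagen carried the whole 1-log gap, power at alpha 0.01 would be about 95% pooled and 56% with country. This too stands. It is why the pooled analyses should stay and a null adjusted result should be read as inconclusive.

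Third, the single-titer figure is not the planned repeated-measures model, and for decay a constant level gap gives no excess. Both are true. They limit how firmly the size can be stated, and they show why the target needs fixing.

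Fourth, Section 9.4.7 allows other demographic variables in models of immune response. It does not name country and does not reach the two analyses with LN architecture as outcome.

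Finally, a within-country comparison is still observational. It removes Uganda–Minnesota differences but not confounding within Uganda, so caution applies to adjusted results as well.

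**Conclusion.** The concern holds. The three analyses have no country-adjusted or stratified companion, and a pooled association from them cannot be assigned to infection or LN damage. Confidence in this omission is high.

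The best-grounded size is for collagen against a single peak titer: 35–44% at p<0.01 with no within-country link, against about 1% with country. It rests on the protocol's preliminary collagen data and its 1-log planning gap. The repeated-measures range (6–73%) depends on the assumed ICC and on which visits carry the gap. The helminth and component figures show direction only: with 10% of Ugandans infected there is essentially no excess, and at high prevalence it is very large. The primary comparison of peak titer is not affected.

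This should be fixed before analysis. It is a gap in what the results can support, not an invalid test.

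**What to change.** Keep the pooled analyses and prespecify beside them:

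1. **PathSeq and LN:** linear regression with gender, country and the five component scores.
2. **LN and antibody:** mixed model with measurement time, gender and country, permuting LN measures within country. State whether level or decay is tested. If decay, add LN-by-time and country-by-time terms and name the visits used.
3. **Helminths and LN:** a country-stratified (van Elteren) test, which becomes a within-Uganda Mann-Whitney test if no Minnesota participant is infected.
4. **Reporting:** present pooled and adjusted results as complementary, label pooled ones as including between-country differences, and do not attribute a pooled-only association to infection or LN damage.

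Other pooled models in Sections 9.4.3 and 9.4.9 (the sparse canonical correlation, lasso, CD8-function and immune-function models) also lack a country term, so the same rule could be considered there for consistency.

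The cost is SAP wording and analysis time, with no added participants, samples or visits. The drawback is power. At alpha 0.01, adjusted power for a within-country correlation of 0.3, 0.4 or 0.5 is about 27%, 56% or 83% for LN against a single titer, and 24%, 50% or 79% for one component against LN. For an assumed 1 SD helminth effect within Uganda it is about 5%, 36%, 44%, 35% or 4% with 3, 9, 15, 21 or 27 of 30 infected; an exact test raises the two extremes to roughly 11–12%. Adjustment also removes any part of the country gap truly caused by infection. A null adjusted result is therefore inconclusive, and the protocol should say so.
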